#### **2.2.1 Location of the study**

The clinical trial will be carried out at the Rehabilitation Center of the Military Police of the State of Rio de Janeiro

#### **2.2.2 Protocol pre -registration**

After approval by the UNISUAM Research Ethics Committee, the entire clinical trial protocol will be registered in the Brazilian Registry of Clinical Trials ( ReBEC - <https://ensaiosclinicos.gov.br/> ) or in the *Clinical trials* ( <https://clinicaltrials.gov/> )

## **2.3 Sample**

The sample will consist of 60 participants, divided into two groups: an intervention group (n=30) that will do a 12-week program, 2x/week of Pilates method exercises , and a control group (n=30) that will not do any intervention for rehabilitation in the period.

### **2.3.1 Study recruitment site**

Patients will be recruited at the Central Hospital of the Military Police and at the specialized multidisciplinary outpatient post-COVID-19 follow-up.

### **2.3.2 Inclusion criteria**

1. Patients with a previous diagnosis of COVID-19, who required hospitalization and required invasive mechanical ventilation for at least 7 days and who were discharged between August and December 2021 to minimize regression to mean;
2. Both sexes;
3. Older than 18 years.

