Most often described as a manifestation of tiredness, lack of energy or exhaustion associated with impairment in the performance of usual day-to-day activities, the current definition of fatigue describes it as a symptom resulting from an underlying pathophysiology or resulting from a specific treatment. performed, then fatigue is understood as a sequel, which proves to be refractory to the usual energy recovery strategies. The fatigue symptom is very prevalent in clinical situations such as oncological diseases, heart failure, fibromyalgia and chronic obstructive pulmonary disease, in addition to conditions related to the frailty of the elderly (MOTA *et al.*, 2005; WINTER & FOWLER, 2009).

In this context, a recent study found that while the symptom burden in individuals recovering from hospital admission with COVID-19 generally improved at initial follow-up, 53% reported persistent shortness of breath, 34% persistent cough, and 69% persistent fatigue (MANDAL *et al.*, 2020). already Perrin *et al.* (2020) described these persistent symptoms as fatigue, diffuse myalgia, depressive symptoms and sleep disturbances comprising a broad spectrum called post-COVID-19 syndrome (PERRIN *et al.*, 2020).

In a recent review of the pathophysiological mechanisms of chronic fatigue in post-COVID-19 patients, the authors defend the premise that post-COVID-19 fatigue syndrome may result from damage to olfactory sensory neurons, causing an increase in resistance to flow. of cerebrospinal fluid (CSF), and further leading to congestion of

the lymphatic system with subsequent toxic accumulation. within the central nervous system (CNS) which could biologically explain the persistence of this symptom. The lymphatic system, described in recent works as a perivascular network, where a large proportion of subarachnoid cerebrospinal fluid circulates , responsible for the drainage of toxic residues from brain metabolism. This whole-brain pathway has been called the “lymphatic system”, based on its similarity in function to the peripheral lymphatic system, and its functions have been described in the pathophysiological scope of Alzheimer's Disease (JESSEN *et al.*, 2015).

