## **1.4 Goals**

### **1.4.1 Primary / General**

To evaluate the clinical and functional effects of a quarterly Pilates Method exercise program for patients with post-COVID syndrome.

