### **2.3.3 Exclusion criteria**

1. Need for supplemental home oxygen;
2. Motor or neurological or cognitive alteration that contraindicates the practice of Pilates .
3. Persistence of clinical signs of deep vein thrombosis
4. Upper limb dynamometry < 14 kg for men and < 7 kg for women would indicate very marked peripheral muscle weakness and would therefore contraindicate Pliates at the moment.

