### **2.3.7 Post COVID functional scale (PCFS)**

The Post-COVID-19 Functional Status Scale is a longitudinal patient assessment tool for identifying changes in post-COVID-19 functional status and their evolution. The PCFS scale covers the entire set of functional areas, in particular limitations in activities of daily living (ADL) and in the workplace, as well as changes in lifestyle. The scale can be administered to the patient by trained staff or conducted by the patient as a self-assessment. In the project, following the guidelines of the PCFS, which will be used for research purposes, it will be conducted by a trained evaluator and followed all the guidelines described for this purpose. This scale consists of six ordinal categories that reflect conditions of increasing severity, from 0 to 4. Death is coded as "D". Grade 0 implies the absence of any residual symptoms. If one or more residual symptoms are present but do not affect the patient's normal activities, grade 1 will be assigned. If they are limited in intensity/frequency or occasionally avoided, grade 2 will be assigned; grade 3 implies limitations that force the patient to reprogram usual activities, reflecting the inability to perform some of them, which, in fact, must be performed by others. Grade 4, the most severe, is reserved for severe functional restrictions that require continuous assistance in daily activities (CORSI *et al.*, 2020; KLOK *et al.*, 2020) .

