### **2.5.4 Confounding variables**

The length of stay and the degree of dysfunction acquired in the ICU may represent confounding variables. Thus, avoiding regression to the mean, inclusion in the study can only occur after 3 months (90 days) after hospital discharge. This is the time described to minimize eventual complications inherent to the immobility syndrome and homogenize the groups

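### No entry criterion requires a persistent symptom, so a ventilated COVID-19 survivor at PCFS grade 0 can enter a trial whose question is about post-COVID syndrome

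*Combined protocol and SAP*

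**What the plan says.** Section 2.3.2 has three inclusion criteria. The first takes "Patients with a previous diagnosis of COVID-19, who required hospitalization and required invasive mechanical ventilation for at least 7 days" with discharge between August and December 2021. The second allows both sexes. The third is "Older than 18 years".

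Section 2.3.3 excludes home oxygen, alterations that contraindicate Pilates, persisting signs of deep vein thrombosis, and marked weakness ("Upper limb dynamometry < 14 kg for men and < 7 kg for women"). Section 2.5.4 adds a timing rule: "inclusion in the study can only occur after 3 months (90 days) after hospital discharge". Section 2.3.1 names two recruitment sources, the Central Hospital of the Military Police and a "specialized multidisciplinary outpatient post-COVID-19 follow-up".

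The question is framed differently. Section 1.4.1 sets out to evaluate the effects of "a quarterly Pilates Method exercise program for patients with post-COVID syndrome". Both hypotheses in 1.5 name the same patients, and the expected results in the Summary refer to people who have symptoms of the syndrome. The Summary and 1.3 describe the syndrome by symptoms that last well beyond the acute illness.

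On the main functional scale, 2.3.7 states: "Grade 0 implies the absence of any residual symptoms". PCFS is one of four components of the primary outcome (2.4.1). mMRC is a secondary outcome (2.4.2). The Fatigue Pictogram is collected (2.3.9) and fatigue appears in the hypotheses, but 2.4 does not list it.

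**The concern.** The entry criteria describe a past event, severe ventilated COVID-19. The question describes a present state, persistent symptoms. Nothing in the plan connects the two. If fully recovered survivors are enrolled, the trial will draw a conclusion about post-COVID syndrome from a sample that partly lacks it.

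There is also a measurement consequence. A patient at the best grade of a 0 to 4 scale can only stay there or get worse, so any benefit could show only as less worsening. Enough such patients would pull the group difference on PCFS, dyspnoea and fatigue towards zero. A null result on symptoms could then mean either that Pilates did not help or that there was little to treat.

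**Working it through.** **1. Can a symptom-free patient enter?** Take a survivor at PCFS 0 and mMRC 0 with normal grip.
- Inclusion (2.3.2): ventilated at least 7 days, discharged in the window, adult. Met.
- Exclusion (2.3.3): no home oxygen, no contraindicating alteration, no thrombosis signs, grip above the cut-offs. None applies. All four remove people who are too unwell; none removes a recovered person.
- Timing (2.5.4): at least 90 days since discharge. Met by waiting.
- Recruitment source (2.3.1): a place of recruitment, with no symptom rule attached.

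The patient is eligible. Under 2.3.7, and under grade 0 in Annex 1, the same patient has no residual symptom and so falls outside the protocol's own description of the syndrome.

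**2. Is recovery by entry plausible?** Discharge falls in August to December 2021 and recruitment in April to May 2022 (2.8). The shortest interval is 31 December to 1 April, 91 days. The longest is 1 August to 31 May, about 10 months. Section 1.1.8 says respiratory abnormalities may resolve within 6 to 12 months or become permanent. Recovery by entry is therefore possible; how often it occurs is not given.

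**3. Which outcomes have a floor for this patient?**
- PCFS (primary component): yes, at grade 0.
- mMRC (secondary): yes, if at grade 0.
- Fatigue Pictogram (objectives and hypotheses): yes, if at the lowest level.
- Handgrip, quadriceps 1RM and quadriceps endurance (the other three primary components): no. A symptom-free person can still gain strength or endurance.
- SF-36 (secondary): eight domains scored 0 to 100; not fixed at the best score by PCFS 0.

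**4. Is the stated sample size affected?** Reproducing 2.5.1:
- d = (41.3 + 4.7 − 41.3) / 5.05 = 4.7 / 5.05 = 0.93.
- Two-sample t-test, two-sided alpha 0.05, power 0.80: n = 19.16 per group, rounded to 20.
- 20 × 1.2 = 24 per group, 48 in total.

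The figure reproduces. Its endpoint is quadriceps maximum load, which has no floor at PCFS 0, so the gap in the criteria does not make it wrong.

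**5. Can the symptom-free share be taken from the background?** Section 1.1.9.5 cites a cohort recovering from COVID-19 admission in which "53% reported persistent shortness of breath, 34% persistent cough, and 69% persistent fatigue".
- Without breathlessness: 100 − 53 = 47%.
- Without cough: 100 − 34 = 66%.
- Without fatigue: 100 − 69 = 31%.
- Free of all three: at most the smallest of these, 31%. It could be 0%, because 53 + 34 + 69 = 156, which exceeds 100.

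The range of 0% to 31% covers three symptoms in a general admitted cohort. PCFS 0 is stricter, since Annex 1 also rules out pain, depression and anxiety related to the infection, and this trial takes only patients ventilated for a week or more. The range is not an estimate for this sample.

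**The case against.** The strongest reply is that symptom-free entrants will be rare. A week or more of ventilation and recruitment partly through a post-COVID clinic both point that way. This stands as mitigation but does not close the gap. The clinic is one of two sources, attendance is not a symptom criterion, and the plan neither shows nor requires that entrants have symptoms. If they are rare, the missing criterion costs almost nothing to add.

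A second reply is that randomisation should spread such patients evenly on average. That is correct: the problem is who the result applies to and possible dilution, not a biased comparison.

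A reader might infer more in three ways, and the documents do not support any of them.
- *That power drops by a calculable amount*, found by shrinking d = 0.93 by the share at the floor. That d belongs to quadriceps load. The plan gives no effect size or standard deviation for PCFS, mMRC or fatigue, claims no power on them, and gives no share. The 47% and 31% above are single-symptom shares from a broader cohort.
- *That these patients cannot improve on the trial's outcomes in general.* Three of the four primary components have no such floor.
- *That mMRC 0 means no syndrome.* Annex 2 allows breathlessness on strenuous exercise at grade 0, and fatigue or weakness may persist. Only PCFS 0 is defined as symptom-free.

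**Conclusion.** The concern holds as a mismatch between the population named and the population admitted. It rests on the text alone and needs no assumption about numbers: following the plan exactly can enrol people outside the named syndrome and still produce a conclusion about it.

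The measurement consequence is limited to PCFS and, where the patient is also at the best grade, mMRC and the Fatigue Pictogram. Its size cannot be stated, because the share of entrants at PCFS 0 is unknown and 2.4.1 does not say how PCFS is combined with the three muscle tests. The comparison between arms remains unbiased in this respect and the sample-size calculation stands. This should be corrected, at small cost, but it does not invalidate the design.

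**What to change.** Preferred: add to 2.3.2, *at least one residual symptom attributed to COVID-19 at baseline (PCFS grade 1 or higher), assessed before randomisation*. PCFS is already administered by a trained evaluator, so no new instrument is needed. The order matters, because a rating made after allocation is known could influence who enters. This aligns entry with the named syndrome and removes the PCFS floor. It does not remove the mMRC or fatigue floors: a fatigued patient at mMRC 0, or a breathless patient without fatigue, would still enter.

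The cost is extra screen failures in a pool limited to a five-month discharge window. With an assumed share s at PCFS 0, enrolling 48 means screening 48 / (1 − s): about 54 at 10%, 60 at 20%, and 70 at 31%.

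If that is not acceptable, restate the objective, hypotheses and conclusion as applying to survivors of ventilated COVID-19 with or without persistent symptoms, and report the baseline PCFS and mMRC distributions by arm. That costs wording and one table.

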### **2.3.3 Exclusion criteria**

1. Need for supplemental home oxygen;
2. Motor or neurological or cognitive alteration that contraindicates the practice of Pilates .
3. Persistence of clinical signs of deep vein thrombosis
4. Upper limb dynamometry < 14 kg for men and < 7 kg for women would indicate very marked peripheral muscle weakness and would therefore contraindicate Pliates at the moment.

### **2.3.4 Risks and Benefits**

The possible risks of this research are, the increase in the sensation of shortness of breath during the execution of the exercises, the reduction of the saturation of O2 and, the possible muscular pains resulting from the practice of the Pilates Method .

As benefits we can mention: the improvement of the disposition to carry out the activities of daily living, the improvement of the balance, in addition to obtaining gains in relation to the quality of life and the reduction of dyspnea.

The research will be immediately suspended if any risk or damage to the health of the subject participating in the research is perceived, resulting from it, not provided for in the consent form (ICF). If it is proven that a group has benefited from the intervention of the protocol of this work, the same intervention will be offered to the other group, avoiding any harm to the patient.

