## Summary

**Introduction:** COVID-19 is an emerging pandemic disease caused by severe acute respiratory syndrome (SARS-CoV-2). Although most patients infected with SARS-CoV-2 are asymptomatic or have mild symptoms, some patients develop severe symptoms that can long-term impair their quality of life and functional capacity. SARS-CoV-2 is closely related to severe acute respiratory syndrome (SARS) with direct and indirect effects on several systems, especially the musculoskeletal system, in addition to the respiratory system. Some of these symptoms persist for a long time, called Post-Covid-19 Syndrome, directly interfering with the functional capacity and quality of life of these patients. Pilates exercises focus on breathing, postural symmetry, trunk stabilization, flexibility, joint mobility and strengthening through the full range of motion of all joints and not isolated muscle groups. **Objectives:** The objective of this study will be to evaluate the clinical and functional effects of a Pilates exercise program for patients with Post-Covid-19 syndrome after a period of intensive care admission and invasive mechanical ventilation. **Methods:** The study will be a clinical, randomized and controlled trial. 48 patients of both sexes, over 18 years of age, who have developed the severe form of COVID-19 and required at least 7 days of invasive mechanical ventilation will be recruited. Patients who currently require supplemental oxygen at home and who present motor, cognitive or neurological alterations that prevent the practice of Pilates will be excluded. They will be previously randomized in a 1:1 ratio by electronic system and blindly allocated to the intervention group that will perform an exercise protocol based on the Pilates method, 2x/week, for 12 weeks in therapeutic sessions of identical protocols lasting 60 min. All patients will be evaluated before and after for peripheral muscle strength and endurance, post-Covid-19 functional status, dyspnea, fatigue and quality of life. Data analysis will be performed using the SPSS 23.0 program ( *Statistical Package for Social Sciences* ). Descriptive analysis will be performed for all variables (mean and standard deviation). *General Linear Model* ( GLMs ) with mixed design will be performed to compare treatment effect size between groups. The *pairwise comparison comparisons* ) will be performed to verify the mean difference between the Pilates Group and the Control Group in all variables in each period independently. Intention-to-treat analysis was used using the *Last method. observation Carried Forward* (LOCF) for lost participant data. A significance level of 0.05 and a confidence interval of 95% will be adopted. **Results:** The expected results are based on the alternative hypothesis that Pilates exercises are clinically effective, improving functional performance, exercise tolerance, balance, reducing symptoms and improving the quality of life of patients with symptoms of Post-Covid-19 Syndrome.

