## 2.4.2 secondary outcome

Improved quality of life (Questionnaire SF36) and reduced perception of dyspnea during physical activities and ADLs ( mMRC and Borg ).

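### No adverse-event collection or analysis is described for either arm, and between assessments only the Pilates arm has a described route by which events would be noticed

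*Combined protocol and SAP*

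**What the plan says.** Section 2.3.4 (Risks and Benefits) names three possible risks: more breathlessness during the exercises, a fall in oxygen saturation, and muscle pain from Pilates. It then makes two provisions.

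- **Suspension.** "The research will be immediately suspended if any risk or damage to the health of the subject participating in the research is perceived", limited to harm that is "not provided for in the consent form (ICF)".
- **Offer to the other arm.** "If it is proven that a group has benefited from the intervention of the protocol of this work", then "the same intervention will be offered to the other group, avoiding any harm to the patient". This sentence sets no harm condition.

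The outcomes in 2.4 are efficacy measures. The primary outcome combines the PCFS with grip dynamometry and quadriceps strength and endurance. The secondary outcome is "Improved quality of life (Questionnaire SF36) and reduced perception of dyspnea during physical activities and ADLs", measured by mMRC and Borg. Section 2.5.5 specifies a mixed-design general linear model, pairwise comparisons and LOCF. It mentions no harms.

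On contact, 2.5.3 and 2.3.11 give the Pilates arm two therapist-led sessions a week for 12 weeks. Section 2.3 describes a control group "that will not do any intervention for rehabilitation in the period". Both arms share the assessments: "All patients will be evaluated before and after for peripheral muscle strength and endurance", along with functional status, dyspnea, fatigue and quality of life (Summary).

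**The concern.** A trial that foresees extending its intervention to the other arm should be able to say what happened to patients on both sides of the ledger. Here one side is undefined. The visible text contains no adverse-event definition, form, collection time or analysis.

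What comes to light informally will also be uneven. A physical therapist sees each Pilates patient twice a week. No trial contact is described for a control between the first and last assessment. If events noticed in sessions were reported as they arose, Pilates would look worse than it is. If nothing were recorded, it would look safer than anyone had checked. In neither case could a reader compare the arms on events the outcome scales do not capture. Information not collected at the 12-week visit is hard to recover at analysis.

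**Working it through.** **1. Contacts per patient.** Inputs: two sessions a week for 12 weeks (2.5.3), all led by a physical therapist (2.3.11); no rehabilitation for controls (2.3); assessments before and after in both arms (Summary).

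- Pilates, between assessments: 2 x 12 = 24. Controls: 0 described.
- Including assessments: 24 + 2 = 26 against 2.

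These are contacts that the protocol describes, not all clinical observation.

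**2. What the common assessments can show.**

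| Event | Covered in both arms by |
|---|---|
| Persistent breathlessness | mMRC (2.3.8) |
| Persistent fatigue | Fatigue Pictogram (2.3.9) |
| Lasting pain | SF-36 pain domain (2.3.10); PCFS wording (Annex 1) |
| Loss of function; death | PCFS, where death is coded D (2.3.7) |
| Falls, muscle or joint injury | No item described |
| Unscheduled care, admission | No item described |
| Events resolved within the 12 weeks | No item described |

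Two details narrow the upper rows. Borg is listed as a secondary outcome in 2.4.2, but 2.3.8 confines it to Pilates sessions, so the only symptom measure between assessments exists in one arm. And with two assessments, LOCF carries baseline forward for anyone lost, so a patient who left because of harm would be scored as unchanged.

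Desaturation is a named risk and an oximeter is budgeted (2.7), but no saturation reading is scheduled or analysed.

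**3. What the suspension rule adds.** It is worded for any participant, but excludes harms foreseen in the consent form. The form was not available for review. The ethics checklist (Appendix 2, c.1) requires it to state possible risks. If it repeats the three risks in 2.3.4, those fall outside the rule. The rule also describes no recording.

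**4. Effect of unequal ascertainment (assumed rates, not in the documents).** Recorded events = n x true risk x proportion captured. Take n = 24, a true risk of 20% in both arms, and 90% capture in the Pilates arm:

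- Pilates: 24 x 0.20 x 0.90 = 4.3.
- Controls: 24 x 0.20 x 0 = 0 with no capture; 24 x 0.20 x 0.25 = 1.2; 24 x 0.20 x 0.50 = 2.4; 24 x 0.20 x 0.90 = 4.3.

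Equal risks look unequal until capture is equal.

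**5. Precision with good collection.** With zero events in n patients, the exact one-sided 95% upper limit is 1 - 0.05^(1/n).

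- n = 24 (2.5.1): 1 - 0.05^(1/24) = 11.7%.
- n = 30 (2.3): 1 - 0.05^(1/30) = 9.5%.

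Both are shown because 2.3 and 2.5.1 give different group sizes. That conflict needs reconciling but does not alter this point.

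For a formal comparison, the two-sided Fisher test at 0.05 with 24 per arm has power of about 10% for assumed risks of 10% against 20%, and about 31% for 10% against 30%. Harms should therefore be described, not tested against a threshold.

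**The case against.** **Harm is not visible in one arm only.** A reader might infer that harm could surface only among Pilates patients and that worsening in controls would go unseen. The documents contradict this. Both arms are assessed before and after on mMRC, the Fatigue Pictogram, PCFS and SF-36, so lasting worsening of breathlessness, fatigue, pain or function has a comparator. This objection stands and confines the point to what those scales miss.

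**The closing phrase of the offer need not be a safety claim.** In translated text, avoiding harm may mean only that controls should not lose out by having gone untreated. That reading is at least as natural, and the point does not depend on the other one.

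**Safety is not ignored.** The suspension sentence covers any participant, and consent-form text that may bear on harms was not available. This stands as a limit on what can be said. It does not supply a recording procedure or analysis in the protocol itself.

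**Controls may be seen elsewhere.** Section 2.3.1 recruits through a specialised post-COVID outpatient follow-up. But nothing describes routing events noticed there into the trial data.

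**The cited symptom frequencies prove little.** Section 1.1.9.5 reports that "53% reported persistent shortness of breath, 34% persistent cough, and 69% persistent fatigue". It is tempting to turn these into expected counts per arm. They come from another cohort at initial follow-up, whereas this trial enrols patients ventilated for at least 7 days and at least 90 days after discharge (2.3.2, 2.5.4). Fatigue is also not a risk named in 2.3.4. They are not used here.

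**The trial is too small for safety conclusions.** True, but that is a reason to state the limits, not to leave events uncollected.

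**Conclusion.** The point holds in a limited form. The visible protocol describes no collection or analysis of adverse events in either arm. Between assessments, events have a described route to notice only in the Pilates arm, 24 supervised sessions against none. The trial could therefore make no fair between-arm statement on falls, injuries, unscheduled care, admissions or transient events, although 2.3.4 foresees extending Pilates to controls if benefit is shown.

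This rests on two assumptions: that the unavailable consent form contains no structured harms collection, and that no trial contact with controls is planned beyond what is written.

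Two stronger inferences are not supported. The text does not show that the protocol asserts Pilates to be harmless. The remark in 1.3.2 about adding Pilates to public-health practice is a statement of relevance, not a trial decision.

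This is a cheap and worthwhile improvement to data collection. It does not threaten the efficacy comparison.

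**What to change.** 1. **Collection (2.4 and the existing 12-week assessment).** Add one short fixed harms checklist, asked in the same words in both arms over the same 12-week recall: new or worse breathlessness, muscle or joint pain, falls, unscheduled medical care, admission, death.
2. **Analysis (2.5.5).** Report it descriptively by arm with confidence limits, stating the zero-event upper limit for the group size finally adopted. Report events noticed in sessions separately, as a description of the Pilates arm only.
3. **Wording (2.3.4).** Clarify what the phrase about avoiding harm means, and state that harms information will be reported alongside benefit. The decision on the offer stays with the investigators and the ethics committee. It should not be tied to a low-powered comparison.

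Cost: one page, about 5 minutes per patient at a visit already planned, and one descriptive table. The downside is imperfect 12-week recall, which should be similar in both arms.
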